2.1 Characterizing geometric uncertainty in treatment delivery

For spinal SBRT, accuracy in patient positioning is the cornerstone of providing safe and high quality treatment. Previous work from our institution underscored the importance of precise patient set-up, permuting delivered treatment plans to account for potential setup error, and demonstrating that a 2mm translational error can lead to >5% loss of tumor coverage, and greater than 25% increase in the maximal dose to the organs at risk (16).

Our current practice employs the Brain Lab ExacTrac targeting system (17, 18) which uses floor-mounted kV imagers to acquire a pair of orthogonal oblique films, which are used

(sometimes in conjunction with external locator devices) by the system software to compare the patient's position relative to the treatment planning dataset on the basis of bony anatomy. Based on this software fusion, the system calculates the required couch shifts to achieve optimal patient alignment, which are executed through a robotic couch system. Next, the coordinates of the final isocenter are verified using a CT-on-rails system to acquire a three-dimensional dataset. In-house software (19) is used to perform a 3D-3D fusion of the datasets, which then allows computation of the deviation from the planning CT, with tolerances for translation and rotational error of 1 mm and 2 degrees, respectively. Our current practice thus uses the ExacTrac system software to calculate the necessary couch corrections based on algorithmic alignment of bony anatomy alone. However, the ExacTrac software also has the capability calculate patient position based on implanted fiducial markers, provided that the markers are present at the time of CT simulation. Based on our extensive experience with the ExacTrac system, we observe that the bony fusion based calculations excel at detecting translational set-up errors, but can yield discrepancies in assessing rotational error (roll, pitch, yaw). We hypothesize that the addition of implanted fiducials will improve setup accuracy, particularly with regard to rotational error.

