2.3 Incorporation of lessons learned to date

As of this revision (Version 8), we have accrued 7 patients into Stage 1 of the protocol (five in group 1, and two in group 2). In reviewing our data to date, we conclude that the residual alignment error as calculated using either the bony fusion algorithm or implanted fiducial methods are in good agreement, with no significant difference between the methods (Figure 1).

[figure not shown]

Figure 1: Left panel - Examining the differences in the calculated error in each dimension using both fusion and fiducials reveals good agreement (average difference near zero). Right panel - RMS analysis demonstrates no statistical or clinically meaningful difference.

Extending our analysis, we have performed offline 6D fusions of the CT-on-rails-datasets with the simulation data sets, and conclude that fiducials are no better than the bony fusion algorithm for correcting rotational error (Figure 2).

[figure not shown]

Figure 2: Using offline 6 dimensional fusion, an accurate assessment of residual rotational error can be performed. RMS analysis demonstrates no significant difference in performance between the two approaches.

An additional development has been the migration of our spinal SBRT treatments to a new linear accelerator, with upgraded capabilities (e.g. 6D robotic couch correction, cone-beam CT, and improved fusion algorithm). These new capabilities will further improve the overall accuracy of patient setup with respect to rotational error. As we have demonstrated that any difference between the fusion approach and the fiducial approach has thus far been too small to detect, we believe that the improved platform would further close the hypothetical gap between the approaches, and that we will not be able to observe it.

Thus, going forward, we will:

- Remove the fiducial component from the protocol

- Prospectively enroll additional patients (without the need for fiducials) to characterize the accuracy of the new treatment platform, including a group of patients with tumors in the cervicothoracic junction (who were not originally included because of challenges with fiducial placement)
- Perform a retrospective study of setup accuracy in patients with cervicothoracic junction tumors as historical controls

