We will use descriptive statistics to summarize the demographic and clinical characteristics of patients enrolled in this study. We will similarly summarize Dmax, D5cc, central lumen dose, and full thickness dose for each patient group (defined above).

We will use the methods of Bland and Altman (43) to compare the positioning of the isocenter with respect to 6 directional orientations (superior-inferior, anterior-posterior, lateral-medial, pitch, roll, and yaw) using the implanted fiducial markers and using our standard practice for each patient group. We will similarly compare the 3-dimensional distance from the isocenter as calculated using the implanted fiducial markers and using our standard practice. We will also estimate these paired differences (fiducial – standard practice) with 95% confidence intervals, and we will estimate with 95% confidence intervals the correlation between the measures made using the fiducial markers and those made using standard practice. We will similarly analyze Dmax, D5cc, central lumen dose, and full thickness dose for each patient group.

We will tabulate adverse events by grade for each patient group.

Sample Size

We will test whether the paired difference (fiducial – standard practice) in 3-dimensional distance from the isocenter is significantly different from 0. A sample size of 10 patients in each patient group will give us 80% power to detect an effect size of 1 standard deviation with a 2-sided significance level of 0.05. A sample size of 10 patients will also give us 82% power to

detect a correlation between the 2 methods of estimating the position of the isocenter of at least 0.80 using a 2-sided significance level of 0.05. These sample size calculations were performed with nQuery Advisor ® 7.0 (Copyright © 1995-2007, Statistical Solutions, Saugus, MA).

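### In Groups 5-7, section 8.0 has no set-up endpoint that can be computed and covers rotation: its one powered difference test is a fiducial comparison of 3-dimensional distance, which rotation about the isocenter leaves unchanged

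*Combined protocol and SAP*

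**What the plan says.** Objective 1.2 is to describe the six-dimensional set-up accuracy of ExacTrac. Section 2.1 credits bony fusion with good detection of translational error, reports discrepancies for rotation, and continues: "We hypothesize that the addition of implanted fiducials will improve setup accuracy, particularly with regard to rotational error". Section 2.3 removes fiducials, moves treatment to a new accelerator and says of it: "These new capabilities will further improve the overall accuracy of patient setup with respect to rotational error". Section 5.1 closes Groups 1 and 2 and opens Groups 5, 6 and 7, ten patients each, without fiducials.

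Section 8.0 was not rewritten to match. Under Sample Size, the test is whether the paired difference, fiducial minus standard practice, "in 3-dimensional distance from the isocenter is significantly different from 0". The power claim is "A sample size of 10 patients in each patient group will give us 80% power", the effect being 1 SD of the paired difference at two-sided 0.05. A second power figure, 82%, is given to "detect a correlation between the 2 methods of estimating the position of the isocenter of at least 0.80".

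Under Analysis, Bland-Altman methods are planned for "6 directional orientations (superior-inferior, anterior-posterior, lateral-medial, pitch, roll, and yaw"), again fiducial against standard practice. The 3-dimensional distance is listed there as a further, separate quantity. The paired differences and the correlations are to have 95% confidence intervals.

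Section 5.6 adds that the cone beam CT will give independent six-dimensional information on the accuracy of the couch correction. Section 8.0 does not say how that information will be analysed.

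**The concern.** The question is mainly about rotation, and the one difference singled out for a test and a power statement appears to be purely translational. The distance is listed apart from pitch, roll and yaw, so its natural meaning is the length of the three-axis translation. A patient rotated about a correctly placed isocenter then scores no error.

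The larger difficulty lies in the open groups. The distance test, the powered correlation, and the comparisons and intervals for the six axes all need a fiducial reading and a standard reading on the same patient. Groups 5-7 supply only the standard reading. What is at stake is objective 1.2 on the new platform: thirty patients could be enrolled with no pre-specified summary of the dimension in which the platform is expected to do better.

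**Working it through.** **1. The plan's own power figures.** Inputs from section 8.0: n = 10, effect 1 SD of the paired difference, two-sided 0.05.

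- Paired t-test, noncentral t with 9 degrees of freedom and noncentrality 1 × √10 = 3.162: power 80.3%, against 80% stated.
- Correlation of 0.80 by Fisher z: Φ(atanh(0.80) × √7 − 1.96) = Φ(1.0986 × 2.6458 − 1.96) = Φ(0.947) = 82.8%, against 82% stated.

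Both figures are sound for n = 10 pairs. The effect is in SD units, so the 80% would hold equally for any single rotational axis.

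**2. Does the distance respond to rotation?** Assumption: distance = √(x² + y² + z²) of the residual translation at the isocenter. A rotation about the isocenter does not move the isocenter. With an assumed offset of 0.5 mm per axis, the distance is √(3 × 0.25) = 0.866 mm at 0, 1, 2 and 3 degrees.

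**3. What rotation does away from the isocenter.** Displacement = 2r sin(θ/2), where r is the distance from the isocenter perpendicular to the rotation axis. The angle is the 2-degree tolerance in section 2.1. The documents give no value for r, so the values below are assumptions.

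| r (assumed) | Displacement at 2 degrees | Change in tested distance |
|---|---|---|
| 20 mm | 0.70 mm | 0 mm |
| 30 mm | 1.05 mm | 0 mm |
| 50 mm | 1.75 mm | 0 mm |

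**4. Effect on the test.** Simulation, 20,000 trials of n = 10, assumed values: both methods equally accurate in translation, with a true difference of 1 SD on one rotational axis. The distance test rejects in 4.7% of trials, which is its type I error. A paired test on that axis rejects in 80.4%.

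**5. Would adding three rotational tests be the answer?** At unadjusted 0.05, three independent tests carry a familywise error of 1 − 0.95³ = 14.3%. With Bonferroni (0.05/3 = 0.0167), power per axis at n = 10 falls to 60.4%, and 80% needs n = 14. Such tests would still need fiducials.

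**6. What Groups 5-7 can supply.** Without fiducials there is no fiducial-minus-standard difference. Section 5.6 does give a six-dimensional residual of ExacTrac against cone beam CT for each patient. For a mean residual on one axis, with one value per patient, the 95% half-width is t(0.975, 9)/√10 = 2.262/3.162 = 0.72 SD.

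**The case against.** The strongest reply is that rotation is already handled. Section 8.0 compares pitch, roll and yaw by Bland-Altman methods and, on the natural reading, gives each paired difference a 95% interval. Such an interval carries the same inference as an unadjusted two-sided 5% paired t-test. Section 2.3 also reports offline six-dimensional fusions and a rotational RMS analysis in the 7 fiducial patients, and finds fiducials no better than bony fusion. All of this stands. A reader might infer that rotation goes unanalysed, or that a translational null would be taken as proof of rotational accuracy. The documents support neither inference. Section 2.1's hypothesis is also about set-up accuracy in general, with rotation emphasised.

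Three further inferences should be resisted.

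- Subtracting unsigned distances is not a fault for an accuracy question. Two methods each 1 mm off in opposite directions are equally accurate, and their 2 mm disagreement would show in the signed axis comparisons.
- No section says that the historical-control study in section 2.3 will use this distance, so it cannot be said to inherit the problem.
- Section 2.1's coverage and organ-dose figures are for a 2 mm translational error. They do not size the effect of a rotation.

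It can also be said that the test belongs to a closed comparison, so its endpoint hardly matters now. The first half is right, and it is why the point concerns Groups 5-7: once the fiducial comparisons fall away, section 8.0 puts nothing in their place.

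**Conclusion.** The concern holds in a limited form. The one difference test that section 8.0 names and powers does not respond to rotation about the isocenter, provided that 3-dimensional distance means the translation length, which the plan does not define. Rotation has planned interval estimates, but they are fiducial comparisons that Groups 5-7 cannot provide. The open groups are therefore left without a usable set-up endpoint that covers rotation, although objective 1.2 and section 2.3 call for one.

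The size is illustrative: 0 mm on the tested distance against 1.05 mm at an assumed 30 mm for a 2-degree rotation (0.70 to 1.75 mm over 20 to 50 mm). The stated 80% and 82% power reproduce, but they describe a comparison that the open groups will not make. This is a gap in the specification, and the planned imaging is enough to close it.

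**What to change.** In section 8.0, for Groups 5-7:

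- Make the main set-up endpoint the residual error of ExacTrac against cone beam CT, from the six-dimensional data of section 5.6. Report residual pitch, roll and yaw with the three translations.
- Add one summary: the largest displacement of fixed, pre-defined points at the ends of the treated vertebra under the combined residual translation and rotation. Describe the results against the 1 mm and 2-degree tolerances of section 2.1. Do not test this length, or the length of a vector difference, against 0, because a length cannot be negative.
- Replace the power sentence with a precision statement: 10 patients give a 95% half-width of about 0.72 SD for a mean residual. Say how multi-fraction patients, whom Stage 1 allows, are reduced to one value each.
- Define 3-dimensional distance by formula wherever it is kept.
- Use the same endpoint for the historical controls only where six-dimensional data exist; the documents do not show that they do.
- Label any re-analysis of the 7 fiducial patients post hoc, since their results have been seen.
- Label any lever arm used for illustration as an assumption.

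The cost is a short extra calculation and a restated precision figure, with no new imaging in Groups 5-7.

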5.0 Treatment Plan

5.1 Summary of study design

Our overall study plan consists of two stages. In the first stage, we will seek to characterize the accuracy of our new treatment platform and perform analysis of the ExacTrac positioning system.. Four dimensional CT datasets are recommended for simulation will also allow us to use data from this portion of the protocol to characterize the degree to which organ at risk (OAR) motion is relevant at each spinal level. In this stage, we will now close accrual to

Groups 1 (T4-T12 with fiducials) and 2 (L1-L5 with fiducials) and begin enrollment in three new groups of 10 patients each:

Group 5: tumors from C5-T3

[figure not shown]
Group 6: T4-T12

Group 7: L1-L5

Patients in groups 5-7 will not undergo gold fiducial placement. In this stage of the study patients will be treated with the standard dose constraints to normal tissues.

In the second stage, we will seek to characterize the tolerance of the esophagus to hypofractionated radiation doses through prospective constraint relaxation and toxicity monitoring. In this stage, we will seek to accrue 20 additional patients in two groups of 10, to be filled sequentially with progressive constraint relaxation (Group 3: T4-T10 / constraint level 2, Group 4: T4-T10 / constraint level 3). The data collected from Group 1 in the first stage of the protocol will give us data on the dose delivered to the esophagus under our current practice guidelines (which are commensurate with the guidelines of the multicenter RTOG 06-31 trial (12), and will serve to verify the safety of our current practice. The second stage of the protocol will accrue in parallel with stage 1. Once Group 3 has completed accrual, patients will be prospectively monitored for a period of 3 months for signs of adverse esophageal toxicity before Group 4 opens. The dose constraints that will be used for Groups 3 allow higher dose than is used in our practice at MD Anderson, but comply with published guidelines for SBRT treatment (29). The dose constraints for Group 4 represent a modest increase of esophageal dose maximums from these guidelines, but the maximum esophageal dose falls well under the maximum allowed on the current RTOG 0813 trial (37). Detailed dose constraint parameters are

enumerated in Section 5.6.2, below. In total, the study seeks to accrue 40 patients. The overall trial schema is summarized below.

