5.6 Set-up verification

On the day of treatment, patients will first be set up on the treatment table as per our standard practice. Once the patient has been positioned by the treatment team, the ExacTrac software will calculate couch correction based on bony fusion of kV images with the treatment planning CT scan. These couch corrections will be transmitted to the patient couch, and the ExacTrac software will re-verify. Next, the cone beam CT will be used to perform a verification scan. In-house 3D-3D matching software will be used to verify the position of the final treatment isocenter. This procedure represents our current clinical practice, and is unchanged for this protocol. The cone beam CT dataset will also provide independent, 6-dimensional information on the accuracy of the calculated couch correction.

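### Section 8's positioning test, agreement analysis and both power figures need fiducial pairs, which Groups 5-7 (30 patients) cannot supply

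*Combined protocol and SAP*

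**What the plan says.** Section 8.0 states one hypothesis test: "We will test whether the paired difference (fiducial – standard practice) in 3-dimensional distance from the isocenter is significantly different from 0". Its sample-size paragraph continues: "A sample size of 10 patients in each patient group will give us 80% power to detect an effect size of 1 standard deviation", at a "2-sided significance level of 0.05". A second statement, "A sample size of 10 patients will also give us 82% power to", concerns detecting a correlation of at least 0.80 between the two positioning methods. Under Analysis, the same section plans Bland-Altman comparisons on six axes, paired differences with 95% confidence intervals, and a correlation. All of these set fiducial against standard practice, within each patient group. The dose metrics follow directly: "We will similarly analyze Dmax, D5cc, central lumen dose, and full thickness dose for each patient group".

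The design sections say something different. Section 2.3 reports 7 patients accrued (five in Group 1, two in Group 2), finds no meaningful difference between the methods, and decides to "Remove the fiducial component from the protocol". Section 5.1 closes Groups 1 and 2, opens Groups 5, 6 and 7 with 10 patients each to characterize the new platform, and states: "Patients in groups 5-7 will not undergo gold fiducial placement". Section 5.6 describes bony fusion followed by a verification scan, and adds: "The cone beam CT dataset will also provide independent, 6-dimensional information on the accuracy of the calculated couch correction".

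**The concern.** A statistical section should say how the data being collected will answer the current objectives. Here the only inferential analysis takes as input a measurement that the patients now being enrolled for set-up accuracy will not have. The purpose of Stage 1 is now the accuracy of the new platform (Objective 1.2). For that purpose the section names no quantity to estimate and no summary. It does not say how repeated set-ups in multi-fraction patients are handled, and it gives no applicable reason for 10 per group. If this stays open, those choices are made after the residuals have been seen, and a reader could take the 80% and 82% figures to describe groups to which they do not apply.

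**Working it through.** **Inputs.** From Section 8.0: n = 10 per group, effect 1 SD of the paired difference, two-sided alpha 0.05, 80% power; and correlation 0.80, n = 10, 82% power. From Section 2.3: 5 and 2 patients in Groups 1 and 2. From Section 5.1: 3 × 10 = 30 patients in Groups 5-7, no fiducials. Assumption: the correlation is tested against 0, since the plan states no null value.

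**Step 1: reproduce the plan's figures.**
- Paired t-test: noncentral t with n − 1 = 9 degrees of freedom and noncentrality 1 × √10 = 3.162. Power is 80.3% (stated 80%).
- Correlation by Fisher z: Φ(atanh(0.80) × √(10 − 3) − 1.96) = Φ(1.0986 × 2.6458 − 1.96) = Φ(0.947) = 82.8% (stated 82%). Using the exact critical r of 0.632 gives 82.6%. Simulating the t-test of r gives about 87%, so the stated figure matches a Fisher-type approximation.

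Both figures hold for 10 complete fiducial pairs in a group.

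**Step 2: count the pairs.**

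| Group | Patients | Fiducial pairs available | Power at 1 SD |
|---|---|---|---|
| 1 (closed) | 5 at Version 8 | at most 5 | 40.1% |
| 2 (closed) | 2 at Version 8 | at most 2 | 9.3% |
| 1 and 2 pooled | 7 | at most 7 | 60.0% |
| 5, 6, 7 | 10 each planned | 0 | not computable |

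The powers use the same noncentral t formula with noncentrality √n. For 80% power the effect would have to be 1.69 SD at n = 5 and 1.28 SD at n = 7. Correlation power at 0.80 by Fisher z is 34% at n = 5 and 59% at n = 7.

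**Step 3: what 10 patients deliver for ExacTrac against cone beam CT.** This assumes one value per patient and roughly normal residuals.
- Mean residual: t(0.975, 9)/√10 = 2.262/3.162 = 0.72 SD half-width of the 95% interval.
- Each 95% limit of agreement: 2.262 × √(1/10 + 1.96²/18) = 2.262 × √0.3134 = 1.27 SD half-width.
- SD: √(9/χ²) at the two 9-df chi-square quantiles gives 0.69 to 1.83 times the estimate.
- If all 30 patients were pooled, which assumes a common distribution across spinal regions, these become 0.37 SD, 0.65 SD and 0.80 to 1.34.

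**Step 4: compare Section 8.0 with Section 5.1.** The Study Plan paragraph of Section 8.0 still describes Stage 1 as adding an interventional radiology procedure, and the Safety paragraph still lets Group 2 accrue during Stage 2. Section 5.1 closes Group 2 and requires no such procedure in Groups 5-7. These statements need to be reconciled.

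**The case against.** The strongest reply is that Stage 1 now aims to characterize accuracy, which is a descriptive task that needs no test. The cone beam scan will supply independent six-dimensional data, and Section 2.3 shows the team already summarizing residual error by root mean square and offline six-dimensional fusion. That much stands: the data are planned and a working method exists. But Section 8.0 limits its descriptive summaries to patient characteristics and dose metrics, plus adverse event tables. It gives none for positioning residuals without fiducials, and the only reasons offered for 10 per group are the two fiducial power statements.

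A reader might also go further than the documents allow, in five ways:
- **That the 30 patients have no analysis at all.** Not so. Demographics, per-group dose summaries, adverse event tables and spinal tumor progression-free survival (Section 7.0) need no fiducials.
- **That the primary test has failed.** No test or endpoint is labelled primary; this is simply the only hypothesis test stated.
- **That Objective 1.4 has no analysis.** Section 8.0 plans descriptive dose summaries, and Section 5.4 plans re-contouring at each respiratory phase. The gap is narrower: the summaries are not said to be motion-inclusive, and the further dose analysis inherits the fiducial pairing.
- **That the 1 mm and 2 degree tolerances are set for the new platform.** Section 2.1 gives them for the CT-on-rails practice, and Section 5.6 does not restate them.
- **That Groups 3 and 4 certainly lack fiducials.** Sections 2.3 and 5.6 suggest it, but only Groups 5-7 are named.

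**Conclusion.** The point holds, and the text is wrong as written rather than merely short on detail: Section 8.0 prescribes, for each patient group, a comparison that Section 5.1 makes impossible in Groups 5-7. The 80% and 82% figures are correctly calculated but apply to no group now being enrolled for set-up accuracy. Those groups supply 0 of 30 pairs, and the closed fiducial groups reach about 40% and 9% power at 1 SD. Objective 1.2 on the new platform has no stated positioning analysis and no applicable sample-size rationale. The figures for Groups 1 and 2 assume that accrual stopped at the Version 8 counts and that every patient gives a usable pair. The conclusion for Groups 5-7 needs neither assumption.

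**What to change.** Rewrite Section 8.0 for Groups 5-7.

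1. **Positioning.** Compare the ExacTrac bony-fusion result with the six-dimensional cone beam CT result. Report mean residual, SD and 95% limits of agreement per axis and group. Use one value per patient, or a patient random effect where several fractions contribute. If the proportion within tolerance is reported, say that 1 mm and 2 degrees come from the CT-on-rails practice and confirm whether they apply to the new platform.
2. **Sample size.** Withdraw the 80% and 82% statements for these groups and give the precision from Step 3 instead. Present it as attained precision. It does not show that 10 is enough, because the plan sets no target width.
3. **Dose metrics.** Replace the inherited fiducial pairing with phase-contoured dose against average-CT planned dose, in patients who have a 4D CT. Sections 5.1 and 5.3 recommend 4D CT without requiring it, so this is a subset of unknown size.
4. **Fiducial comparison.** Report it descriptively for the Group 1 and 2 patients only.
5. **Consistency.** Reconcile the Study Plan and Safety paragraphs with Section 5.1. State also how the retrospective cervicothoracic controls announced in Section 2.3 will be analysed, since Section 8.0 does not mention them.

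The cost is amendment wording and modest analysis work on data already planned for collection. The sponsor also gives up the power figures for a less favourable statement of precision.
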